11.1 Informed Consent	30
12.0 Regulatory Standards.....	30
12.1 Electronic case report forms	30
12.2 Clinical and Regulatory Monitoring.....	30
12.2.1 Study Conduct (Site)	30
12.2.2 Adherence to Reporting Requirements	31
12.3 Participant Confidentiality	31
12.4 Records.....	32
13.0 References	32
Appendix A. Grading of Averse Events	36
Appendix B. Schedule of Events.....	38
Appendix C. Sexual Encounter Profile (SEP).....	39
Appendix D. International Index Erectile Function.....	40

List of Figures

Figure 1: Regulation of Myocyte Tone.....	8
Figure 2. Interaction of Maxi-K channel and nitric oxide. See text for explanation.....	10

List of Tables

Table 1. - Final Dose – h Maxi-K	16
Table 2. Statistical Power	29

Protocol Synopsis

Title	A Double-blind, Placebo-controlled, Parallel Design, Randomized Phase 2A Trial Evaluating the Potential Activity and Safety of hMaxi-K Gene Transfer in Males with Erectile Dysfunction
Study Number	ION 04-ED
Clinical Study Phase	Phase 2A
Number of Centers	One site
Study Objectives	To evaluate the safety and efficacy of a single intracavernous injection of hMaxi K (8000 µg and 16000 µg) or placebo upon penile rigidity or erection in males with erectile dysfunction longer than six months that is attributable to an underlying, stable medical condition.
Study Design	This study is a double-blind, placebo controlled, parallel design, Phase 2A study evaluating the potential activity and safety of a single administration of hMaxi-K (8000 or 16000 µg) or placebo (PBS sucrose 20%) injected into the corpus cavernosum of the penis in men who have been unable to tolerate, do not wish to continue, or have had unsuccessful results with, prior therapy for ED.
Study Participant Population	The study population is men with erectile dysfunction attributable to an underlying, stable medical condition but who are otherwise in good health. The target population is men with erectile dysfunction and those who have been unable to tolerate, do not wish to continue, or have had unsuccessful results with, prior therapy for ED and with an erectile function domain score of IIEF >10 and < 21 at screening and baseline.
Study Procedures	Following screening and study drug administration at week 0, eligible participants will be evaluated at weeks 1, 4, 8, 12, and 24. At each study visit, participants will have a physical examination including examination of the penis (all visits), vital signs, electrocardiogram (ECG) (all visits). Laboratory evaluations including chemistry and hematology will be done at V1, 3, 4, 6, and 7. Urinalysis will be done V1, 2 (prior to dosing), 3, 4, 6, and 7. Endocrine parameters and PTT, PT, sed rate and CRP will be evaluated at Visit 1, 3 and 7. The participant will complete the erectile function domain of the IIEF and Sexual Encounter Profile (SEP) at screening/baseline and at V2, (SEP and IIEF at V2 prior to dosing) V3, V4, V5, V6, and V7. In all participants, plasma specimens will be collected to assay for the presence of hSlo DNA by PCR (V2-V7). These will be kept frozen at -20°C or less at the site for eventual assay by Sponsor.
Primary Study Outcomes	The primary outcome measures will include the Erectile Function (EF) domain of the International Index of Erectile Function (IIEF), Sexual Encounter Profile (SEP), Questions 2 and 3 from SEP. The IIEF EF domain has a 30-point total score, where higher scores reflect better erectile function. SEP is a diary in which participants record each sexual attempt made throughout the study. The two questions from the Sexual Encounter Profile (SEP) deal with the ability to achieve vaginal penetration (SEP2), and the ability to maintain an erection long enough for successful intercourse (SEP3). The erectile function domain category of the IIEF will be used to evaluate the change in erectile status from baseline following

**Secondary
Study
Outcome****Study Duration****Study Start****Sample Size****Statistical
Analysis**

administration of *h*Maxi-K. Change from baseline on the six questions of the IIEF's Erectile function domain category at every visit after administration of study drug will be calculated and compared among the two dose and one placebo groups.

Safety will be assessed by analysis of adverse experiences, and abnormal findings on clinical laboratory tests, electrocardiogram, and physical examinations.

6 months per participant (approximately 1 year to enroll all participants)

TBD

35 participants; N=11 on 8000 µg; N= 11 on 16000 µg; N= 13 on placebo

Both the safety data and data to assess activity will be presented as means and standard deviations or medians and ranges as appropriate for continuous data, and analyzed using either paired t- or Wilcoxon Sign Rank tests for within group changes, and with mixed effects or marginal models to determine differences in trends among the three cohorts over time. Incidence of adverse events will be presented as relative frequencies within groups.

Introduction

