1.6 Clinical Data

2.0 Objectives

The primary objective of this study is to evaluate the safety of a single intracavernous injection of *h*Maxi-K (either 8,000 or 16,000 µg) compared to placebo in males with erectile dysfunction longer than six months that was attributable to an underlying, stable medical condition upon penile rigidity or erection in males with erectile dysfunction longer than six months that is attributable to underlying, stable medical condition.

The secondary objective of this study is to evaluate the efficacy of a single intracavernous injection of *h*Maxi-K, either 8,000 or 16,000 µg, compared to placebo.

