10.3 Analysis of Endpoints

The methods described in this section will be updated during the course of the study. The final version of the statistical analysis plan (SAP) will be issued before the treatment code is broken.

This double blind, phase 2A study is designed to evaluate the safety and efficacy of a single injection of *h*Maxi-K (8000 and 16000 µg) compared to placebo in individual participants. Both the safety data and data to assess efficacy will be analyzed using summary descriptive statistics for the two cohorts and the total study population. Associations between study therapy and the outcomes will be assessed using-repeated measures analyses, and explored in multivariate models, as needed.

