 **Clinical laboratory tests**

The following laboratory tests will be performed at different visits as indicated in the flow chart in [section 3](#) above

- Hematology including complete blood count (CBC) with differential
- Chemistry
- Urine Analysis
- Endocrine Tests

All results corresponding to laboratory evaluations will be presented in IU units. The laboratory results will be listed by treatment cohorts, subject and visit. Abnormal results will be flagged as H or L based on values being above or below the normal range respectively. Values within the normal ranges will be flagged as N.

The frequency of number of incidences of laboratory abnormalities will be displayed by parameter and treatment cohort with respect to the classification of values based on the normal range. Descriptive statistics will be presented for laboratory results with respect to treatment cohort and visit. Further, the change from baseline at each post dose visit will be presented descriptively in accordance to the plan of data collection. Descriptive statistics for the change from baseline to the last available on treatment visit will also be presented. Shift tables will be presented for each analyte to assess the change in abnormalities over visits.

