 **Electrocardiogram**

As part of the analysis for this safety endpoint, in addition to the analysis suggested in [section 9.2](#) above, changes from baseline at each post dose visit will be presented. Number and percentage of subjects reporting abnormalities will further be tabulated with respect to treatment cohort and visits for both the over reader and site evaluations. Shift tables will also be presented to study the change in abnormalities over the visits.

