 **Physical examinations and vital signs**

In addition to the analysis mentioned in section 9.2, the descriptive statistics for change from baseline at post dose visits will be presented for the below parameters

- Heart rate
- Blood pressure
- Weight
- Oral Temperature

Further, the number and percentage of subjects reporting abnormalities for above parameters and during physical examination of the penis will be tabulated with respect to treatment cohort and visits.

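### Safety compared with placebo is a stated objective, but the visible plan defines no active-minus-placebo difference for any continuous safety measure

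*Protocol*

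**What the plan says.** **Objective.** Protocol 2.0 states: "The primary objective of this study is to evaluate the safety of a single intracavernous injection of" *h*Maxi-K, at either dose, "compared to placebo in males with erectile dysfunction longer than six months". SAP section 4 makes efficacy and safety of 16,000 µg against placebo primary, and safety of either dose against placebo secondary.

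**Analysis promised.** The Statistical Analysis entry of the synopsis begins "Both the safety data and data to assess activity will be presented as means and standard deviations or medians and ranges as appropriate". The same sentence goes on to within-group tests and then to a comparison of groups "with mixed effects or marginal models to determine differences in trends among the three cohorts over time". Protocol 10.3, just after naming safety and efficacy data together, adds: "Associations between study therapy and the outcomes will be assessed using-repeated measures analyses".

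**Analysis specified.** Protocol 10.3.1 reduces safety to tabulation. SAP 9.4 then gives:
- laboratory tests: "the change from baseline at each post dose visit will be presented descriptively in accordance to the plan of data collection", plus abnormality frequencies and shift tables;
- ECG: "changes from baseline at each post dose visit will be presented", plus abnormality counts and shift tables;
- vital signs: "the descriptive statistics for change from baseline at post dose visits will be presented for the below parameters", plus abnormality counts.

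The t-tests, repeated measures ANOVA, repeated measures logistic regression and ANCOVA in SAP 9.3 are all assigned to IIEF or SEP.

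**The concern.** A comparative objective needs a comparative estimate. With by-arm changes alone, a reader who wants the drug's effect on QTcF, blood pressure or potassium must subtract group means by hand and has no interval for the result.

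By-arm change is also not a clean measure of drug effect in this schedule. No chemistry is drawn at Visit 2, so under the SAP's baseline definition (last value before treatment) the chemistry baseline is the screening sample. Protocol 7.1 specifies that sample as fasting; no fasting is stated for Visits 3, 4, 6 or 7. The 1- and 2-hour ECGs and the 15-minute vital signs at Visit 2 follow an intracavernous injection. Shifts shared by all arms are therefore plausible, and the placebo arm removes them only if a difference is taken.

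The measures matter on the protocol's own account. Section 5.2.1 names increased potassium efflux, with lower intracellular calcium and altered smooth muscle function in several organ systems, as the potential mechanism of toxicity. Section 9.5 sets individual QTcF triggers. A shift common to all arms could be read as a drug effect, or a moderate drug effect as none, with nothing to show what 35 men can exclude.

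**Working it through.** **1. The plan's own figure.** The documents size the trial for efficacy only: difference 10.0 − 6.6 = 3.4, SD 2.5, alpha 0.05/3 = 0.0167, power 80%. With allocation ratio r = 11/13 and a two-sided normal approximation, placebo n = (1 + 1/r)(z₁₋α/₂ + z₀.₈)² SD²/δ² = 2.18 × (2.394 + 0.842)² × 6.25/11.56 ≈ 12.4, so 13 on placebo and 11 per dose. This matches the planned 11/11/13. Attrition: 35/0.90 = 38.9, so 39 against the stated figure of about 40. No figure is given for any safety comparison, and none of this sizing is in dispute here.

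**2. Is a safety difference defined anywhere in the visible text?**
- SAP section 7: chi-square or exact tests for incidence rates. These do not cover continuous measures.
- SAP section 9, opening text: comparisons of the doses, and of total active, with placebo, and 95% limits on all estimated differences. No safety variable or method is named.
- SAP 9.3: methods for IIEF and SEP only.
- SAP 9.4: by-arm description.
- SAP section 10: the list of tables is not shown, so a contrast there cannot be ruled out.

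The 95% limits therefore have no defined continuous safety difference to apply to. SAP 9.4 also speaks of post-dose visits, which leaves it unclear whether the post-dose readings within Visit 2 get a change from baseline at all.

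**3. What the planned arms could estimate.** For a difference in mean change at one time, the 95% half-width is t₀.₉₇₅,df × SD × √(1/n₁ + 1/n₂):
- one dose v placebo, 11 v 13 (df 22): 2.074 × 0.410 = 0.85 SD;
- pooled active v placebo, 22 v 13 (df 33): 2.035 × 0.350 = 0.71 SD;
- one dose v placebo after about 10% loss, 10 v 12 (df 20): 2.086 × 0.428 = 0.89 SD.

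With an assumed SD of QTcF change of 10, 15 or 20 ms, one dose v placebo gives 8.5, 12.7 or 17.0 ms, and pooled active gives 7.1, 10.7 or 14.2 ms.

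**4. How many intervals?** Modelling every scheduled post-dose reading would mean 7 times for QTcF (1 h, 2 h, Visits 3 to 7), 13 for each of heart rate, systolic and diastolic pressure (8 readings over 2 hours plus 5 visits), and 4 for each of potassium and calcium: 7 + 39 + 8 = 54. Two dose contrasts give 108 intervals; adding pooled active gives 162. Collapsing the eight Visit 2 vital-sign readings to one value gives 7 + (3 × 6) + 8 = 33 times, hence 66 intervals for the two doses and 99 with pooled active. If there were no effect, about 99 × 0.05 ≈ 5 would exclude zero by chance.

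**The case against.** The best defence is that SAP 9.4 follows the operative safety section, protocol 10.3.1, and that protocol 10.3 expects the SAP to update the methods. That stands. A reader might infer that the SAP alone breaks a protocol commitment, but the conflict already lies inside the protocol: the synopsis and 10.3 on one side, 10.3.1 on the other.

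A reader might also infer that the trial's primary question gets no comparison at all. The documents do not support that. Safety alone is primary only in protocol 2.0; the synopsis names IIEF and SEP as primary outcomes, and the SAP makes efficacy and safety of 16,000 µg jointly primary. Adverse events, abnormality counts and shift tables are to be shown for active, split by dose, beside placebo. The gap concerns continuous measures.

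Two further arguments should not be used:
- The instruction to eat breakfast on the dosing day does not bias the Visit 2 ECG changes, because the pre-dose ECG is taken at the same visit. It cannot affect chemistry, because none is drawn then.
- Comparing these intervals with narrower within-arm ones is beside the point, because the SAP plans no within-arm interval for safety.

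Finally, wide intervals and many of them are a fair objection to modelling every reading. They are a reason for a short list and plain labelling. They do not justify leaving the difference unestimated, since a wide interval shows what the trial cannot exclude.

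**Conclusion.** The point holds as a cheap improvement. Safety against placebo is an objective in both documents, a between-group analysis that includes safety data is promised in two places in the protocol, and the visible SAP text defines no such estimate for a continuous safety measure. The claim is textual and does not depend on the sizing. It is subject to the unseen table list.

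The precision on offer is limited: about 0.85 SD either side for one dose and 0.71 SD for pooled active. The millisecond figures rest on the assumed SD of 10 to 20 ms. All the half-widths are for an unadjusted comparison at one time with complete data; baseline adjustment would replace the SD by a residual SD.

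**What to change.** In SAP 9.4, for QTcF, heart rate, systolic and diastolic pressure, potassium and calcium:
- Report the baseline-adjusted difference from placebo in change from baseline, for each dose and for pooled active, with two-sided 95% limits and no hypothesis tests.
- Do this at each scheduled post-dose visit where the measure is taken, and at the 1- and 2-hour Visit 2 ECGs.
- Summarise the 15-minute Visit 2 vital signs by one prespecified value, for example the mean or the maximum change over the 2 hours.
- Target the difference at each time and not a difference in trends, because a single injection can shift a level without a slope. The synopsis's mixed model can supply this; name its covariance structure.
- State that the intervals are descriptive and unadjusted for multiplicity, so some will exclude zero by chance.

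Then reconcile the synopsis and protocol 10.3 and 10.3.1 with SAP 9.4. Declaring continuous safety data descriptive throughout would also remove the contradiction, but would leave the comparative objective without an estimate.

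The cost is SAP and protocol wording, a few extra tables and wide intervals. No new data are needed.

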1.1 Overview

Erectile Dysfunction (ED) is a disease defined as the inability to achieve or maintain an erection sufficient for satisfactory sexual function. ED is a common and significant problem that afflicts approximately 20 – 30 million men in the United States and 150 million men worldwide.¹⁻⁴ Overall, 52% percent of men have some degree of erectile dysfunction and 25% of 75-year old men have complete erectile dysfunction. The disease has a significant negative impact on the quality of life of the patient and their sexual partners and can cause depression and a feeling of inadequacy.

The most common cause of ED is advanced age. Proposed causes of age-induced ED include reduction of NO production, increased contractility of the smooth muscle of the penile corpora, increased myofilament calcium sensitivity due to altered *Rho* kinase expression/activity, and reduction in the relative percentage of smooth muscle fibers and an increase in collagen content thus decreasing the compliance of the cavernous tissue.⁵⁻⁸ The second most common cause is diminished blood flow to the penis due to cardiovascular disease.

ED can either be reversible or nonreversible. Men over 50 years tend to have permanent causes of ED that are disease-related. The most frequently associated diseases include atherosclerosis, hypertension, anti-hypertensive medications, diabetes mellitus, and pelvic surgery and radiation. Treatment for nonreversible ED include: 1) oral phosphodiesterase inhibitors e.g., sildenafil (ViagraTM); 2) vacuum erection devices; 3) intraurethral alprostadil (MuseTM); 4) intracavernous injection of prostaglandin E1 (CaverjectTM or EdexTM) or a combination of PGE1, papaverine and phentolamine; and 5) surgical placement of penile prosthetic implants for physiological disease. Despite the availability of these therapies, the lack of efficacy, their potential side effects, and the loss of spontaneity (the treatment must be planned and taken or used prior to initiating the sex act) have limited therapy for ED to about 10% of the overall patient population with nonreversible ED.

In younger men (ages 20 – 40), psychological causes for ED often predominate and this reversible form of ED can be treated with sex therapy and the drugs listed above. Current therapies for reversible forms of ED include: 1) sex therapy for psychological disease; 2) correction of endocrine abnormality with appropriate hormone therapy in a small percentage of men (<5%); 3) surgical correction for men diagnosed with Peyronie's disease; 4) penile bypass surgery in men who have suffered pelvic or perineal trauma with injury to the penile arteries. ED as a consequence of all other etiologies (more than 90%) is **not** reversible.

There are many reasons why acceptance by physicians and participants for currently available therapies is limited. Sex therapy has limited efficacy and is only suitable for men with a normal penile function and a psychological cause of the ED. Overall, Vacuum Erection Devices (VED) are effective in about 30% of men who use them, phosphodiesterase inhibitors such as Viagra[®], (sildenafil), Cialis[®] (tadalafil), and Levitra[®] (vardenafil) in about 70%, intracavernous injections in 85%, intraurethral alprostadil in about 40%, and penile implants in over 95%. Medical intervention with drugs is least effective in men with long-standing diabetes because the physiological effects of severe autonomic neuropathy and small vessel atherosclerosis limit the effective action of the medications. Although penile prosthetic implants can be inserted into

nearly every man with ED, the negative stigmata of having an operation and a mechanical erection have limited acceptance of the devices by participants since their introduction in the late 1960's. Furthermore, the rate of infection in penile prosthetic implants is reported between 3 to 9% and inflatable prostheses have a long-term mechanical failure rate of about 10%. Ion

Channel Innovations has developed hMaxi-K to treat ED using the same principal as drugs that have been used since 1982, i.e., treatment with medicines causing relaxation of the penile smooth muscle resulting in rigid erections. hMaxi-K consists of the gene for the α -pore subunit of the maxi-K channel, hSlo, inserted into a plasmid vector. Administration of this gene into the corpora increases expression of the maxi-K channel in the smooth muscle cells and an increased efflux of K^+ across the cell membrane resulting in decreased entry of Ca^{++} ions. This effect on ion exchange across the smooth muscle cells allows the smooth muscle of the corpora to relax; the corporal sinusoids become engorged with blood, and the penis to stay rigid. In preclinical studies, a single administration of hMaxi-K to aging rats with ED has been shown to last at least up to six months.⁹ Furthermore, results from these preclinical studies suggest that expression of the α -pore subunit for the maxi-K channel following administration of hMaxi-K may have a long-term effect on the erectile mechanism.⁹ This activity of hMaxi-K may represent a distinct advantage over current drug therapy for ED where the effect of treatment is temporary.

1.2 Physiology of Penile Erection

In order to better understand ED and the mechanism of action for gene transfer using *hMaxi-K*, a description of the normal function of the penis is useful. Normal erection is a neurovascular event that depends upon proper function of two, well-vascularized cylinders of spongy tissue in the penis: the two corpora cavernosa (the corpora). A third channel, the corpus spongiosum, contains the urethra through which either urine or semen passes but is not involved in causing penile rigidity.

Blood flows into the corpora from two pudendal arteries that emerge from the pelvis and separately fork into two smaller branches, the dorsal and cavernous arteries, and enter the penis. The cavernous arteries are the arteries most responsible for erection. Branches of the cavernous artery enter directly into the endothelial-lined, expandable, sinusoidal spaces that comprise the cavernous bodies. Two other branches of the pudendal artery supply the corpus spongiosum and glans penis. When the penis is flaccid the cavernous arteries are only 0.4 millimeter in diameter while during sexual excitement these arteries will double in diameter. These narrow blood vessels are extremely susceptible to blockage in participants with diseases associated with arterial narrowing, e.g., hypertension and atherosclerosis.

During sexual excitement there is a ten-fold increased blood flow to the erectile chambers of the penis. As the sinusoids fill with blood at systemic pressure the smooth muscle cells within the corpora relax, become compressed by the arterial filling pressure and compress the out flowing veins against the thick elastic covering of the corpora, the tunica albuginea, and a rigid erection occurs. Consequently, the penis function as a tone organ, i.e., when tone is high the smooth muscle cells of the corpora are partially contracted and the penis is flaccid. When the tone is low and the myocytes are relaxed, the penis is fully engorged with blood and becomes erect. However, with increased age, diseases (e.g., diabetes mellitus), or states where the smooth muscle cells fail to relax (e.g., anxiety), the occlusion of venous outflow by the corporal smooth muscle is incomplete with a resultant soft, or partial, erection. Regulation of the state of contraction/relaxation of smooth muscle and its effect on the erectile process depends primarily upon the intracellular concentrations of certain ions, in particular potassium and calcium.

Contraction and relaxation of smooth muscle, is critical to the storage and/or conduit function(s) of hollow organs such as the bladder, gut, blood vessels and penis. K channels play an important role in this process by virtue of their ability to alter the membrane potential and excitability of smooth muscle cells.¹⁰⁻¹² Their primary effect is to modulate Ca^{2+} influx through Ca channels (i.e., L-Type, voltage-dependent). The amount of Ca^{2+} that enters the cell through these channels is a major determinant of the free intracellular calcium levels inside the smooth muscle cell,

[figure not shown]
which in turn, determine the degree of smooth muscle cell contraction. Overall, regulation of the contractile process is organ-specific and modulated by a variety of K channel subtypes.¹³⁻¹⁶ Prominent amongst the K channel subtypes found in smooth muscle is the large conductance, calcium sensitive K channel, referred to as the maxi-K channel. Increased maxi-K channel activity is associated with corporal smooth muscle cell relaxation and penile erection. Moreover, alterations in K channel physiology/function are increasingly being recognized as a major contributing factor to the development of the vascular pathologies associated with diabetes,^{17,18} as well as urogenital disorders, including erectile dysfunction.^{11,14}

Intracellular concentrations of ions and second messengers (e.g., (K⁺, Ca⁺⁺,cAMP, cGMP, etc.) are affected by release of neurotransmitters and in turn the changes can be rapidly propagated from cell to cell through specialized intercellular protein pores called gap-junctions.¹⁹⁻²² The importance of gap junctions to coordinate smooth muscle function cannot be overstated. Even after severe nerve loss such as can occur with diabetes or radical prostatectomy there remains sufficient level of intercellular coupling to allow the corporal tissue to function normally following membrane or receptor stimulation. For example, oral administration or by intracavernous or intraurethral injection of a drug that stimulates the exchange of ions across the cell membranes can allow the penis to become erect. This approach has proven successful with FDA approved intracavernous (EdexTM, CaverjectTM) and intraurethral (MuseTM) injection with prostaglandin E1.

Thus, cellular mechanisms that influence cell membrane potential are of critical importance in regulating the moment-to-moment tone of any organ composed predominantly of smooth muscle whether it is the penis, urinary bladder, blood vessels or gut. The relationship of ions, ion channels, and second messenger interaction in smooth muscle cells is depicted in Figure 1.

Figure 1: Regulation of Myocyte Tone

Regulation of myocyte tone is a multi-component process

Inhibitory interaction of K⁺ efflux and Ca⁺⁺ influx. **Persistent Ca⁺⁺ influx is necessary to maintain myofilament contraction.**

